## 4.4 Quality of CPR Data

An optional component of this protocol involves obtaining quality of CPR data, including depth of chest compression, fraction of time during which compression occurs, and other digital data obtained from these devices. Data will be accepted from participating sites that have chest compression quality measurement capability (e.g., ZOLL R-series, Philips MRx, Physiocontrol LIFEPAK 20e).

• Is your site participating in the quality of CPR component of this study? (Yes/No)

If the answer to this question is yes, all digitally available chest compression data from the quality CPR device will be collected.

### 4.5 Pediatric Survival Outcome Data

- Date and time of ICU discharge
- Date and time of hospital discharge
- Vital Status at time of hospital discharge
  - Alive
  - Dead
- Death Date and Time
- PCPC at ICU discharge and hospital discharge
- FSS at ICU discharge and hospital discharge

# 5 Data Analysis

The first two specific aims of this study each involve demonstration of a significant association between ROSC and hemodynamic parameters. The most formal (and simplistic) hypothesis test will compare the proportions of patients in whom ROSC was achieved, among events with average arterial diastolic blood pressures  $\geq 30$ mmHg versus < 30mmHg (Aim 1) during CPR, and among events with average  $ETCO_2 \geq 20$  mmHg versus < 20 mmHg during CPR (Aim 2).

The definition of "average" in the above statement is multiple, as variables such as average arterial BP will be available for one-minute epochs, for up to the first 10 minutes of CPR, as well as for the final minute of CPR, even if duration of CPR is over ten minutes. We shall define "average" in the following ways:

- 1. Average value during the first one-minute epoch of CPR
- 2. Average value during the last one-minute epoch of CPR, up to 10 minutes after CPR initiation
- 3. Average value during the last one-minute epoch of CPR, regardless of CPR duration
- 4. Average value over (up to) the first ten one-minute epochs of CPR

In addition, we will assess the proportion of total CPR time, during (up to) the first ten minutes of CPR, above which the parameters assessed are at or above, versus below, the arterial BP and  $ETCO_2$  thresholds.

While the study aims will be assessed with respect to all of the above measures, we hypothesize *a priori* that values during the last one-minute period of CPR will be most strongly associated with ROSC. While this would seem to indicate use of definition "3."

above for the primary hypothesis test, it is possible that for events for which ROSC is not achieved despite lengthy CPR, CPR parameters during the final minute may reflect less aggressive efforts as futility of continued intervention becomes apparent. (Limited resources prevent collection of full data for arrests with longer duration of CPR, which is recognized as a limitation of this protocol.) Therefore, to avoid this potential bias, the primary hypothesis tests for Aims 1 and 2 will employ parameters during the final minute of CPR up to 10 minutes (definition "2.") above.

While analyses using other variants of hemodynamic parameters will also be explored, the definition "4." above will be of particular interest as it is unknown whether achieving, versus maintaining, a particular pressure is more important for achieving a favorable outcome. Exploratory analyses will assess which definition is a more powerful predictor of ROSC, overall and stratified by duration of CPR. Since all of these parameter definitions are related and findings are expected to be highly consistent between the different definitions, no adjustment for multiple comparisons will be made in these exploratory analyses, which will be clearly denoted as such. Reporting of results will describe all definitions considered and findings from these investigations.

For Specific Aim 3, 24-hours survival, survival to hospital discharge, and survival with favorable neurologic outcome are the survival outcomes that will be examined. While again various hemodynamic parameter summaries will be considered, we hypothesize a priori that proportion of time that CPR is above acceptable arterial DBP and  $ETCO_2$  thresholds is most strongly associated with the various survival outcomes. The primary analysis will assess the relationship between survival at hospital discharge with proportion of time hemodynamic parameters are at or above the thresholds described for Aims 1 and 2.

Significance of association will be assessed by approaches that take into account the possibility for multiple events during the same hospitalization for the same patient. While rates of ROSC will be reported on a per-event basis, the primary comparison of ROSC rates between subgroups of events will be performed incorporating within-patient correlation. While this is possible to carry out using several approaches, we propose using generalized estimating equations (GEE) within a modified Poisson regression model, as estimation of relative risk and adjustment for other factors is facilitated with this approach (as discussed below). Magnitude of association between the dichotomized parameter levels and outcome will be quantified by calculating relative risk of ROSC, along with 95% confidence interval, for children whose hemodynamic parameter is favorable (e.g., DBP  $\geq$  30mmHg) versus others.

As this study is considered exploratory in nature, a two-sided test with Type I error of 0.05 will be performed separately for each of the two hemodynamic parameters, and again separately for the Aim 3 evaluations.

Beyond this basic analysis, we will examine alternative cut points for the two hemodynamic parameters as predictors of ROSC, and more generally assess their overall association with ROSC, via the use of receiver operating characteristic curves. This approach may determine alternative hemodynamic parameter cut points strongly associated with ROSC; utility of criteria determined in this fashion will require validation in future studies.

It will also be important to determine the association of hemodynamic parameters with outcomes, adjusted for patient risk profile and event characteristics up until the time of arrest. For binary outcomes such as ROSC and survival, multivariable regression models will be used to assess this association. As ROSC and other favorable outcomes are not expected to be rare events, we will analyze this prospective study by estimating the relative risk of an event rather than the odds ratio, using the modified Poisson regression approach. As the number of potential adjustment variables is large relative to the number of events, factors for adjustment will be selected from those showing relatively strong statistical association with each outcome. Specific modeling strategies will be documented in more detail in the Statistical Analysis Plan.

While we will compare absolute values of PCPC and FSS between patient subgroups defined by hemodynamic and other parameters, we also expect to dichotomize these outcome measures for similar analyses. An exploratory outcome measure of interest will be "survival with favorable outcome," which may be defined as discharge alive without substantial worsening of PCPC/FSS relative to pre-event status and discharge alive with PCPC 1-3.

For Specific Aim 4, we will describe the quality of chest compression measurements (compression depth, rate, and fraction of time compressed) during CPR, and measure association with arterial diastolic blood pressure,  $ETCO_2$ , and survival outcomes.

This project will have no formal interim analyses scheduled. It is recognized that accumulating data from this study may be analyzed, for example at annual study updates, for presentation at scientific meetings or to assess magnitude of treatment effects for trial planning, prior to study completion. Care will be taken to ensure that such preliminary analyses do not influence study accrual goals.

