## 3 Study Design

The overall objective of the Pediatric Intensive Care Quality of CPR (PICqCPR) Study is to measure high-fidelity hemodynamic data during CPR in CPCCRN intensive care units, and to evaluate the relationship between these parameters and important clinical outcomes. The PICqCPR Study is a multicenter cohort study of in-hospital intensive care unit pediatric cardiac arrests within the CPCCRN network. The Pediatric Intensive Care Unit (PICU) and Cardiac Intensive Care Unit (CICU) are the only two locations within clinical centers that will be used for subject accrual.

For the purposes of this study, CPR is defined as administration of chest compressions for at least one minute. Return of circulation will be recorded, regardless of whether ECMO was utilized or not. The outcome metric for successful CPR is return of spontaneous circulation (ROSC) for at least 20 minutes duration. Repeat chest compression episodes for the same subject are eligible for inclusion. If a subject sustains ROSC for at least 20 minutes after chest compressions end, and then arrests again, it is considered a separate and new event.

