## 4.3 Hemodynamic Variables

The following variables will be collected once every minute for a maximum of ten minutes prior to the beginning of chest compressions:

- Heart rate
- Systolic arterial blood pressure
- Diastolic arterial blood pressure
- Mean arterial blood pressure
- $ETCO_2$
- Central venous pressure/Right atrial pressure
- Pulse oximetry  $SpO_2$

Waveforms of the following variables will be provided throughout the duration of the first 10 minutes of chest compressions, as well as the last minute prior to the end of chest compressions.

- Arterial diastolic pressure
- Arterial systolic pressure
- Central venous pressure/Right atrial pressure
- $ETCO_2$
- Electrocardiogram (bedside monitor)
- Plethysmography (bedside monitor)
- Pulse oximetry  $SpO_2$
- Actual chest compressions provided per minute

The following variables will be collected once every five minutes for the first 20 minutes after chest compressions have ended:

- Heart rate
- Systolic arterial blood pressure
- Diastolic arterial blood pressure
- Mean arterial blood pressure
- $ETCO_2$
- Central venous pressure/Right atrial pressure
- Pulse oximetry  $SpO_2$

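### The primary exposure for Aims 1 and 2 is taken in the minute that ends in ROSC for successes within 10 minutes, and no key analysis guards against returning circulation raising it

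*Protocol*

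**What the plan says.** Protocol section 5 lists four ways to average DBP and ETCO2. Definition 2 is "Average value during the last one-minute epoch of CPR, up to 10 minutes after CPR initiation", and "the primary hypothesis tests for Aims 1 and 2 will employ parameters during the final minute of CPR up to 10 minutes". Definition 3, the last minute whatever the duration, is passed over because in long failures "CPR parameters during the final minute may reflect less aggressive efforts as futility of continued intervention becomes apparent". Each parameter gets its own test: "a two-sided test with Type I error of 0.05 will be performed separately for each of the two hemodynamic parameters".

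Definitions 1 (first minute) and 4 (up to the first ten minutes) will also be analysed and reported. Definition 4 is singled out because "it is unknown whether achieving, versus maintaining, a particular pressure is more important for achieving a favorable outcome". These comparisons, including the strata by CPR duration, are exploratory. The adjusted models use patient risk and event characteristics up to the arrest, so CPR duration is not among them. For Aim 3 the main exposure is the "proportion of time that CPR is above acceptable arterial DBP and" ETCO2 thresholds, related to survival at hospital discharge.

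Section 4.3 collects waveforms "throughout the duration of the first 10 minutes of chest compressions, as well as the last minute prior to the end of chest compressions"; values after compressions end are recorded separately. In section 3, "CPR is defined as administration of chest compressions for at least one minute". Nothing in the protocol removes beats or seconds after native circulation has returned.

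**The concern.** Under definition 2, both the timing and the content of the exposure depend on how the event ends:

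- CPR of 10 minutes or less, success: the minute that ends in ROSC.
- CPR of 10 minutes or less, failure: the last minute before compressions are stopped without sustained ROSC.
- CPR over 10 minutes, success or failure: minute 10, with CPR still going on.

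If the heart begins to eject before compressions stop, the final-minute average in a short success mixes compression-generated and native pressure. DBP and ETCO2 are then high because circulation is returning. The futility problem that the protocol names lowers values in failures; this one raises them in successes. Both push the relative risk upward, and the cap at minute 10 deals only with the first.

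What is at stake is the reading of a positive primary result. It could mean that higher pressure during CPR goes before ROSC, or that pressure rises as ROSC begins. The planned primary test cannot tell these apart.

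**Working it through.** **1. The protocol's own figures.** The two-proportion formula with continuity correction, two-sided 0.05 and a 60:40 split gives 368 and 483 events (30% vs 45% ROSC; 80% and 90% power) and 103 and 130 (30% vs 60%). These equal the Table 2 entries. At 390 events, power for 30% vs 45% is 0.85 without the correction. The sample size arithmetic is not in question.

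**2. Inputs for the artefact in DBP, with no true association.**
- From section 5.1: N = 390; 60% of events with high DBP (stated there for the event average, not for definition 2); ROSC 30% below the threshold and 45% above it for the 50% effect.
- Derived: overall ROSC R = 0.6 × 0.45 + 0.4 × 0.30 = 0.39.
- Assumed: DBP from compressions X is normal with SD 12. The mean is then 30 + 12 × 0.2533 = 33.04, so that P(X ≥ 30) = 0.60 in successes and failures alike.
- Assumed: native DBP D of 40 or 50 mmHg; native circulation in the last s = 5, 10 or 15 seconds; a share a of 50%, 75% or 100% of successes affected; no failures affected.

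**3. Formulas.** With f = s/60, an affected success has final-minute mean (1 − f)X + fD. It is classed as high if X ≥ (30 − fD)/(1 − f), with probability p.
- P(high | ROSC) = h = 0.6(1 − a) + a·p
- P(high) = H = R·h + (1 − R) × 0.6
- ROSC if high = R·h/H; ROSC if low = R(1 − h)/(1 − H)
- Rejection = Φ((d − 1.96·SE0)/SE1) + Φ((−d − 1.96·SE0)/SE1), where d is the difference in ROSC rates and SE0 and SE1 are the pooled and unpooled standard errors. Events are treated as independent.

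**4. One case in full: D = 50, s = 10, a = 0.75.**
- f = 1/6; cut-off (30 − 8.33)/0.8333 = 26.0; p = 0.721
- h = 0.25 × 0.6 + 0.75 × 0.721 = 0.691
- H = 0.39 × 0.691 + 0.61 × 0.6 = 0.6355
- ROSC if high = 0.2695/0.6355 = 0.424; if low = 0.1205/0.3645 = 0.331; RR = 1.28
- d = 0.0935, SE0 = 0.0513, SE1 = 0.0504; rejection = 44%

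**5. All cases: spurious RR (rejection rate; nominal 5%).**

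| Native seconds | D=40, a=50% | D=40, a=75% | D=40, a=100% | D=50, a=50% | D=50, a=75% | D=50, a=100% |
|---|---|---|---|---|---|---|
| 5 | 1.04 (6%) | 1.06 (7%) | 1.08 (9%) | 1.08 (9%) | 1.12 (13%) | 1.16 (20%) |
| 10 | 1.08 (9%) | 1.13 (15%) | 1.18 (24%) | 1.17 (22%) | 1.28 (44%) | 1.41 (69%) |
| 15 | 1.14 (17%) | 1.23 (33%) | 1.33 (54%) | 1.30 (48%) | 1.52 (84%) | 1.82 (98%) |

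The 100% columns are an upper limit: they cannot occur if any success comes after minute 10.

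**6. A second model without pressures or seconds.** Let c be the share of successes within 10 minutes, and q the share of those otherwise below 30 mmHg that are moved to 30 or above. Then h = 0.6 + 0.4·c·q. Take R = 0.6 × 0.60 + 0.4 × 0.30 = 0.48, the protocol's doubling scenario. With c = 0.75 and q = 0.25, h = 0.675 and H = 0.636; ROSC is 0.509 vs 0.429, RR 1.19, rejection 34%. Over c from 0.50 to 0.90 and q from 0.10 to 0.50, RR runs from 1.04 to 1.62 and rejection from 6% to 97%. With q = 0 there is no artefact.

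No calculation was made for ETCO2 or for Aim 3.

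**The case against.** The strongest reply is that the mechanism is conditional. The window closes when compressions end, so native circulation must return before then, and the protocol does not say for how long. This stands, and it is why only a range can be given.

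Failures may also contain native beats. Section 4.2 lists bradycardia with pulses as a first rhythm, and transition to ECMO with ROSC under 20 minutes as an outcome. This stands too: the table sets contamination in failures to zero, so its values would shrink.

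The other definitions and the duration strata will be reported, the hypotheses speak only of association, and the study calls itself exploratory. This helps in part. Definition 1 is largely free of the problem except in very short events, but definition 4 still includes the terminal minute whenever CPR lasts 10 minutes or less. None of these analyses has a stated role in interpreting the primary test, which has its own 0.05 level and a power claim.

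Several stronger readings are tempting and not supported:
- That most successes are measured in the ROSC minute. The protocol gives no CPR durations, and late successes are sampled at minute 10.
- That this bias is larger than the futility bias. Neither can be sized from the document.
- That 10 to 15 seconds would create the whole planned effect of RR 1.5. No 10-second case reaches it, and at 15 seconds only native DBP 50 mmHg with at least 75% of successes affected does.
- That definition 2 must be replaced as primary. Dropping the terminal epoch removes the shortest events, so inclusion would depend on a duration that may be tied to outcome.
- That Aim 3 is equally affected. Its main outcome is survival at discharge, and in a 2-minute event 10 seconds is 10/120, or 8%, of CPR time.

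**Conclusion.** The point holds as a structural weakness of unknown size. Definition 2 ties the exposure to the outcome in successes within 10 minutes. The protocol considers only reduced effort in long failures, and no planned key analysis separates pressure that precedes ROSC from pressure raised by it. Under a true null at 390 events, the assumed inputs give a spurious RR between 1.04 (5 s, native DBP 40 mmHg, half of successes affected) and 1.82 (15 s, 50 mmHg, all affected), with rejection between 6% and 98%. Apart from N and the section 5.1 rates behind the 39% and 60%, these inputs are assumptions. The result does not show that the primary test will mislead; it shows that the plan as written could not tell if it did. A prespecified key analysis is a sufficient and cheap improvement.

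**What to change.** In section 5, for Aims 1 and 2:
- Prespecify a key analysis using the average over up to the first ten one-minute epochs, leaving out the terminal epoch of every event whatever its outcome. Ending the window a fixed interval before compressions stop is an alternative. Events over 10 minutes keep all ten epochs.
- For events with no earlier epoch, report definition 1 separately. In a one-minute event it coincides with definition 2, so it does not settle the question there.
- State that a definition 2 result is read as pressure preceding ROSC only if this analysis agrees.

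Repeat the exclusion as a sensitivity analysis for the Aim 3 proportion-of-time exposure. Definition 2 can stay primary.

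The cost is wording and a little more analysis; the waveforms are already collected. The shortest events leave the key analysis. Their number and ROSC rate should be reported, because short duration may be related to outcome.

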#### 5.1 Sample Size

Based upon pilot CPCCRN data, approximately 260 CPR events are expected to occur on an annual basis, resulting in approximately 130 events with eligible arterial data (See Table 1: PICqCPR Pilot Data).

Site:	#wks:	#CPR events:	Arterial Catheter at time of CPR:	Eligible Arterial Catheter Data:	Annual Eligible CPR Events with Arterial Catheter Data:
СНОМ	20	13	7(54%)	5(38%)	13
CHOP	20	9	3(33%)	3(33%)	7
CNMC	17.1	21	14(67%)	11(52%)	33
CHLA	19.3	16	8(50%)	8(50%)	21
UCLA	20	9	7(78%)	5(56%)	13
MICH	18	10	7(70%)	6(60%)	17
PHNX	20	11	6(55%)	6(55%)	15
UPMC	20	8	6(75%)	5(63%)	13
Totals:	n/a	97	58(60%)	49(51%)	132

Table 1: PICqCPR Pilot Data
-----------------------------

Further, based upon CHOP limited preliminary data, we can assume that approximately 60% of pediatric CPR events will have average event arterial diastolic blood pressures exceeding 30 mmHg. We must also assume that 30% of events with average arterial diastolic blood pressures less than 30 mmHg will still obtain ROSC, based upon large registry data. Using these conservative estimates, in just one year, we will have

more than 90% power to detect a doubling in likelihood of ROSC ( $\sim 60\%$  ROSC rate) when the event average diastolic pressure exceeds 30 mmHg. However, in light of the higher number of subjects needed to determine if the ROSC rate associated with higher arterial diastolic pressures would be 50% more (a very important clinical effect), 3-4 years may be necessary for more than 80% power to detect a significant effect in the setting of a 50% increase. Because this will be the first study to assess the association of CPR hemodynamics with outcomes in children, we will plan a 3 year study with 390 CPR events.

For additional examples of estimated sample sizes needed for substantial power when these parameters are varied, see Table 2: Sample Size Estimates. (These estimates are approximate, as correlation between multiple events occurring in the same patient may slightly affect power). We do not expect this study to have high power for detecting a significant association between hemodynamic parameters and survival, as effect on patient survival outcomes is expected to be substantially moderated relative to beneficial effect on acute ROSC.

Table 2:	Sample	Size	Estimates
----------	--------	------	-----------

$DBP \ge 30 mmHg:$	$\begin{array}{l} {\rm ROSC} \ {\rm Rate} \\ {\rm if} \ {\rm DBP} \geq \\ {\rm 30mmHg:} \end{array}$	50% Effect; N=80%, 90% power:	100% Effect; N=80%, 90% power:	150% Effect; N=80%, 90% power:
50%	30%	n=352, 460	n=96, 122	n=46, 58
60%	30%	n=368, 483	n=103, 130	n=46, 60
70%	30%	n=424, 550	n=117, 150	n=50, 67

### 6 Data Management

#### 6.1 Electronic Data Capture System

In this study, de-identified waveform data will be provided to the expert reviewers via a secure electronic website which is maintained at the Data Coordinating Center (DCC). All research coordinators and investigators will be trained through an in-person and/or

web-based training session before the start of the project, and topics will include data abstraction, collection, study workflow, and the data entry process.

### 6.2 Data Security

The DCC is located at the University of Utah in Salt Lake City, Utah. The DCC has a state-of-the-art computer infrastructure with a dedicated server room with a fire suppression system, air conditioning, and separate air filtering. The server facility is locked separately from the remainder of the DCC and access to the building is monitored by security personnel year round. The DCC coordinates its network infrastructure and security with the Health Sciences Campus (HSC) information systems at the University of Utah. This provides the DCC with effective firewall hardware, automatic network intrusion detection, and the expertise of dedicated security experts working at the University. Network equipment includes three high speed switches and two hubs. User authentication is centralized with two Windows 2008 domain servers. Communication over public networks is encrypted with virtual point-to-point sessions using secure socket layer (SSL) or virtual private network (VPN) technologies, both of which provide at least 128 bit encryption. The electronic data capture system (EDC) (Web-based collaborative workspace), and other web applications use the SSL protocol to transmit data securely over the Internet. Direct access to DCC machines is only available while physically located inside the DCC offices, or via a VPN client. All network traffic is monitored for intrusion attempts, security scans are regularly run against DCC servers, and DCC IT staff are notified of intrusion alerts.

Servers are backed up daily through a dedicated backup server and internal high speed network. Incremental backups occur hourly and nightly. Full system backups occur nightly and weekly with off-site rotations. Security is maintained with Windows 2008 user/group domain-level security. Users are required to change their passwords every 90 days, and workstations time out after 6 minutes of inactivity. All files are protected at group and user levels; database security is handled in a similar manner with group level access to databases, tables, and views in Microsoft SQL Server.

